To address **Aim 1** (*impact of menopause-related sleep fragmentation on metabolic and behavioral biomarkers of body fat gain*), the mean levels in each endpoint in response to experimentally fragmented sleep (**Hypothesis 1a & 1b**) will be examined using repeated-measures generalized linear mixed-model regression. Models will incorporate the 2 SB contrasts addressing **Hypothesis 1a and 1b** to simultaneously compare the impact of sleep fragmentation in the HF-free, estrogenized environment (**SB_{SF1} vs. SB_{UD1}**), and hypo-E2 environment with stable HF levels (**SB_{SF2} vs. SB_{UD2}**); exploratory analyses will adjust for HF, either categorized (e.g., any versus none) or number of HF. If there is an omnibus effect of experimental sleep fragmentation, we will conduct post-hoc analyses on each SB contrast to explore whether the impact of experimental sleep fragmentation is consistent across hormonal and HF contexts. To address **Hypothesis 1c**, mean levels in outcomes will be contrasted **SP_{UD3} vs. SP_{UD1}** to assess the impact of sleep disruption related to HF in the environment without experimental sleep fragmentation, comparing those developing HF (expected N=26) with those who do not develop HF; analyses will adjust for initial E2 level.

Aim 2 (*impact of HF on metabolic and behavioral biomarkers of body fat gain*) will be examined using a repeated-measures generalized linear mixed-model regression analysis to determine the effect of HF on mean levels of in metabolic and behavioral biomarkers. The regression will include SB contrasts that assess the impact of HF in the presence (**SB_{SF2} vs. SB_{SF1}**) and absence (**SB_{UD2} vs. SB_{UD1}**) of experimental sleep fragmentation. If an omnibus effect of HF is observed, post-hoc analyses will be conducted on each SB contrast to explore whether the impact of HF is consistent across sleep fragmentation contexts. Additional analyses will substitute objectively measured HF or night-time only HF.

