To address **Aim 3** (*impact of estradiol withdrawal on metabolic and behavioral biomarkers of body fat gain*), the mean levels in each endpoint in response to estradiol withdrawal (**Hypothesis 3**) will be examined using repeated-measures generalized linear mixed-model regression. Models will incorporate the 2 estrogenized and hypo-E2 contrasts addressing simultaneously the impact of estradiol withdrawal in the unfragmented and fragmented sleep states. If there is an omnibus effect of estradiol withdrawal, we will conduct post-hoc analyses on each sleep state contrast to explore whether the impact of estradiol withdrawal is consistent across both sleep states. Exploratory analysis will include adjusting for HF – either categorical (yes/no or

none/infrequent/frequent) or continuous – and sleep HF-related disruption in the hypo-E2 state (second SB).

Exploratory Hypothesis #1 analyses will involve a repeated-measures generalized linear mixed-model regression similar to those proposed for the **Hypothesis 1a** analysis using the RQ as an indirect measure of resting EE as the dependent measure, and the same post-hoc paired contrasts and interaction terms for randomization order. **Exploratory Hypothesis #2** analyses will involve addition of interaction terms (between total body fat or visceral adiposity with sleep fragmentation, HF, or E2 withdrawal) to models described for **Aims 1–3**, to test for effect modification on each metabolic or behavioral endpoint. These analyses are by necessity exploratory in nature given the sample size of this complex experimental study. **Exploratory Hypothesis #3** will involve an omnibus repeated-measures regression model encompassing all 6 contrasts described in **Aims 1–3** with the PANAS Negative Affect scale score as the primary predictor and adjustment for fragmented versus undisturbed sleep given an expected association between sleep fragmentation and affect. Post-hoc analyses using paired t-tests on each SB contrast will be conducted to explore the potential variability of the impact of negative affect on each metabolic and behavioral biomarker across the sleep fragmentation, HF, and hormonal contexts. Psychological and cognitive factors driving eating behaviors on the DEBQ will also be explored.

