Sample size: Forty subjects will complete all study procedures. Sample size calculations are based on pilot data correlations between the change in the number of EEG arousals and change in leptin levels from before to after receiving GnRHa. The observed Pearson and Spearman correlations are $r=-0.44$ and $r_s=-0.36$. The detectable correlation is $r=-0.43$ for a sample size of 40 and $r=-0.52$ for the subgroup analysis ($n=26$) in **Hypothesis 1c** ($\alpha=0.05$, 80% power). Because it takes 3 months (screening/menstrual tracking plus 2 months of active procedures) for each subject to complete the study and data analysis time is required after all procedures are completed, accrual is expected to be achieved in the first 39–42 months of the Award. The expected accrual rate of 1.1 subjects per month is therefore similar to that which [REDACTED] achieved in prior healthy volunteer studies with a similar number of in-lab nights. This rate is lower than the 1.7/month that [name] achieved with healthy volunteers to leuprolide studies but with less intensive procedures. To ensure that accrual proceeds as planned, we will advertise widely using postcards we have used to enroll 2.4 women/month to menopause studies and which colleagues used to enroll 2.2 healthy volunteers/month to a study with fewer nights in the sleep lab.¹⁴² Based on previous experience, we expect to consent up to 130 subjects in order to have 40 study completers, given that up to 10 women may not be eligible after completing screening procedures and an additional 8 women may decline to receive leuprolide after completing SB#1, and because some women will participate in pilot procedures only.

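### The stated 80% power is for an arousal–leptin correlation that the SAP does not plan to test, and the n=26 figure given for Hypothesis 1c does not describe its planned group comparison

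*SAP*

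**What the plan says.** The SAP, under Sample size, states the basis of its calculation: "Sample size calculations are based on pilot data correlations between the change in the number of EEG arousals and change in leptin levels". Both changes are those seen across GnRH agonist treatment. The pilot correlations were -0.44 (Pearson) and -0.36 (Spearman). With alpha 0.05 and 80% power, the detectable correlation is given as -0.43 for 40 women, and then as "r=-0.52$ for the subgroup analysis ($n=26$) in Hypothesis 1c".

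The analysis paragraphs plan something else.

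- **Hypotheses 1a and 1b (SAP, Aim 1).** Mixed models compare fragmented with undisturbed sleep in each of the two hormonal states. A gate follows: "If there is an omnibus effect of experimental sleep fragmentation, we will conduct post-hoc analyses on each SB contrast".
- **Hypothesis 1c (SAP, Aim 1).** Between two undisturbed periods, labelled SP_UD3 and SP_UD1, "mean levels in outcomes will be contrasted". The groups are set out as "comparing those developing HF (expected N=26) with those who do not develop HF". It is added that "analyses will adjust for initial E2 level".
- **Aim 2.** The effect of hot flashes on mean biomarker levels is examined through two sleep-block contrasts, again with an omnibus test.
- **Aim 3.** "Models will incorporate the 2 estrogenized and hypo-E2 contrasts addressing simultaneously the impact of estradiol withdrawal". This covers both sleep states, with an omnibus test and post-hoc contrasts.

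The SAP's Analysis approach names fasting leptin as the primary metabolic endpoint and satiety on a VAS as the primary behavioral one.

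**The concern.** A power statement should tell the reader what the planned test can detect. A correlation between two change scores is unaffected by the size of the mean change, so -0.43 says nothing about the mean difference in leptin that 1a or Aim 3 could find. Satiety is not tied to any figure.

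For 1c the two parts of the SAP disagree. The Sample size paragraph treats it as a correlation within 26 women; the Aim 1 paragraph treats it as a comparison of two groups that together make up the whole sample.

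What is at stake is interpretation. If 1a, 1b, 1c or Aim 3 gives a null result, a reader cannot tell from the SAP which differences the test had a fair chance of detecting, and may wrongly attach the printed 80% to it.

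**Working it through.** **Inputs from the documents.** Alpha 0.05, 80% power, n=40 and n=26 (SAP, Sample size); 26 women expected to develop hot flashes (SAP, Hypothesis 1c); about two thirds expected to do so (Protocol, Overview; 2/3 × 40 = 26.7).

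**Derived or assumed.** The comparison group of 14 is 40 − 26. Sidedness is not stated; two-sided is inferred in step 1. The documents give no SD, so results are in SD units.

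**Step 1. Reproduce the printed figures.** By Fisher z, detectable |r| = tanh[(1.960 + 0.842)/√(n − 3)].

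- n=40: tanh(2.802/√37) = tanh(0.461) = 0.431
- n=26: tanh(2.802/√23) = tanh(0.584) = 0.526 (0.518 with the small-sample bias term)

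These match 0.43 and 0.52. One-sided testing would give 0.39 and 0.48, which do not match. The arithmetic is sound.

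**Step 2. Compare the powered quantity with the planned tests.**

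| Hypothesis | Planned test | Does the printed figure describe it? |
|---|---|---|
| 1a/1b | two within-woman mean contrasts, omnibus | No |
| 1c | change in mean level, 26 vs 14 | No; the figure uses 26 women |
| Aim 2 | hot-flash effect on mean levels, two contrasts, omnibus | No; the predictor is hot flashes, not arousals |
| Aim 3 | two within-woman mean contrasts, omnibus | No |

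**Step 3. Hypothesis 1c as a group comparison.** For an unadjusted two-sample t-test on the change score with 38 df, 80% power needs a noncentrality of 2.875, so d = 2.875 × √(1/n1 + 1/n2).

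- 26 vs 14: 2.875 × 0.3315 = 0.95 SD
- 24 vs 16: 2.875 × 0.3227 = 0.93 SD
- 28 vs 12: 2.875 × 0.3450 = 0.99 SD

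This reads SP_UD3 as the undisturbed period of Sleep Block 2. The Protocol describes two sleep blocks, the SAP's other contrasts use only the indices 1 and 2, and no third undisturbed period is defined.

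**Step 4. Omnibus test for 1a/1b and Aim 3.** The SAP does not say whether this is one averaged effect or a joint 2-df test, so both are shown. Assumptions: one value per woman per condition, equal SDs and equal effects in the two contrasts, no covariates, and correlation ρ between the two within-woman differences.

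- Starting point, one paired contrast with 39 df: 2.873/√40 = 0.454 SD.
- Averaged effect: d = 0.454 × √((1 + ρ)/2).
- 2-df test (Hotelling, F with 2 and 38 df): 80% power needs λ = 10.436, where λ = 40 × 2d²/(1 + ρ), so d = √(10.436(1 + ρ)/80).

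| ρ (assumed) | Averaged effect | 2-df test |
|---|---|---|
| 0 | 0.32 SD | 0.36 SD |
| 0.5 | 0.39 SD | 0.44 SD |
| 0.8 | 0.43 SD | 0.48 SD |

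**The case against.** The strongest reply is that the correlation was a reasonable way to choose n, that Hypotheses 2 and 3 in the Protocol's Specific Aims are themselves worded as correlations, and that no result would change. Much of this stands: the pilot correlation may remain as the reason for 40 women, and the defect is one of documentation. But the SAP tests Hypothesis 3 as a mean contrast, Hypothesis 2 concerns hot-flash frequency rather than arousals, and the paragraph assigns a figure to 1c by name.

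A second reply is that a two-group comparison can be written as a correlation. It can, but then n is 40: with p = 26/40 = 0.65, r = 0.953/√(0.953² + 1/(0.65 × 0.35)) = 0.41. The n=26 figure still does not describe it.

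A third is that the replacement figures are approximations too, since the SAP plans mixed models, adjusts 1c for initial E2 and allows other covariates. That is fair, and they must be labelled so.

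Three stronger readings are tempting, and the documents support none of them.

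- *The trial is underpowered.* The documents give no SD or target difference against which to judge that.
- *The printed figure makes 1c look weaker (or stronger) than it is.* The printed correlation uses change in arousals among 26 women; the planned test uses hot-flash status among 40. The predictors differ, so the two values of r are not comparable.
- *Power must also be given for the post-hoc contrasts behind the omnibus gate.* Those are run only "to explore whether the impact of experimental sleep fragmentation is consistent across hormonal and HF contexts". They are exploratory, and a plan need not power them.

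**Conclusion.** The concern holds as a mismatch between the power basis and the planned tests. The printed 80% does not apply to 1a/1b, 1c, Aim 2 or Aim 3; the 1c figure conflicts with the SAP's own description of 1c; and neither primary endpoint has a detectable mean difference.

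The size of what is missing, at two-sided 0.05 and 80% power, is about 0.95 SD of the change score for 1c (0.93–0.99 if 24 to 28 of the 40 develop hot flashes), and 0.32–0.48 SD of the within-woman difference for 1a/1b and Aim 3 across both forms of the omnibus test. The first rests on the unadjusted t-test and on reading SP_UD3 as Sleep Block 2; the second on the assumptions in step 4. No figure is offered for Aim 2, because the SAP does not fix how hot flashes enter that model. The point should be fixed, but it calls neither the sample size nor the design into question.

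**What to change.** Reword the Sample size paragraph of the SAP:

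1. **Hypothesis 1c.** Replace the n=26 correlation with the detectable 26 vs 14 difference in change, about 0.95 SD (0.93–0.99 SD for 24 to 28 women with hot flashes). Label it an unadjusted t-test approximation that ignores the E2 and other covariate adjustment. Correct or define SP_UD3.
2. **Hypotheses 1a/1b and Aim 3.** State whether the omnibus test is an averaged effect or a 2-df test. Give the matching detectable difference (0.32–0.43 SD or 0.36–0.48 SD), the assumed correlation between the two differences, and the simplifying assumptions.
3. **Aim 2.** State that the printed correlation is not the power of these mean-level contrasts either.
4. **Units.** Convert the figures to leptin and satiety VAS units, with the assumed SDs stated.
5. **Pilot correlation.** If it is kept, label it as background to the choice of n, not as the power of a planned test.

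The cost is wording. The sample size, endpoints, models and tests stay as they are. The team must supply SDs for leptin and satiety and a between-contrast correlation, and must declare the form of the omnibus test, which the SAP leaves open.
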